9.5 Physical Examination Data

No physical examination data analysis will be performed in this trial.

9.6 Electrocardiogram Data

For 12-lead ECG parameters, measured values and changes from baseline at each time point and at the time of final IMP administration will be summarized using descriptive statistics.

The numbers and percentages of subjects who have a QTc interval (QTcF) of >450, 480, or > 500 msec at any post-treatment time point until the time of final IMP administration will be calculated. The numbers and percentages of subjects who have a change in QTc interval from baseline of >30 and >60 msec at any post-treatment time point and at the time of final IMP administration will be calculated. Also at baseline and at each post-treatment time point, the numbers and percentages of subjects will be calculated in the same manner as described above.

Shift tables for QTcF interpretation (normal or abnormal) will be prepared at each post-treatment time point and at the time of final IMP administration compared with baseline. Interpretation (normal or abnormal) assessments by the trial site (investigator or subinvestigator) will be used instead of the assessments by the central ECG analysis laboratory.

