3.7.3.3 Physical Examination and Vital Signs

1) Physical examination

The investigator or subinvestigator will check the physical conditions of the subject by interview and other methods at the prespecified time points. The physical examination includes the observation of the head, ears, eyes, nose and pharynx, chest, abdomen, genitourinary tract, extremities, nerves, and skin/mucosae. At the screening examination, the date and the results of assessment will be recorded in the source document and the eCRF. At subsequent assessments, only the date of assessment will be recorded in the source document and the eCRF. A clinically important physical

finding that is absent at the screening examination but observed at any post-treatment assessment will be recorded as an AE.

2) Vital signs (blood pressure, pulse rate, and body temperature)

At the prespecified time points, axillary temperature will be measured after the subject is kept rested according to the procedures specified by the trial site. Blood pressure (systolic and diastolic) and pulse rate will be measured after the subject is kept supine for at least 3 minutes. The measurement result of body temperature should be rounded to the first decimal place for recording, even if the measurement result is shown the second decimal place or more. The date and time, and the results of measurements will be recorded in the source document and the eCRF.

3.7.3.4 12-Lead Electrocardiogram Assessments

At the prespecified time points, a rest 12-lead electrocardiogram (ECG) will be recorded using the ECG monitor provided by the central ECG measurement facility and according to the procedure specified by the facility. However, if the serum potassium concentration at the trial site or the central laboratory is confirmed to exceed 5.5 mEq/L at any time point with no specified 12-lead ECG during the treatment period, an additional 12-lead ECG will be performed as an unscheduled examination. The investigator or subinvestigator will interpret each ECG chart as normal or abnormal, and record the status (measured/ not measured), the date of recording, as well as the interpretation (normal or abnormal [details, if abnormal]) in the source document and the eCRF.

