The ECG record will be sent to the central ECG measurement facility to measure the heart rate, RR interval, PR interval, QRS axis, QT interval, and QTc (QT corrected for heart rate) interval (QTcB, QTcF). The central ECG measurement facility will in turn send the 12-lead ECG analysis report to the investigator or subinvestigator.

The investigator or subinvestigator will reconfirm the interpretation of the 12-lead ECG referring to the analysis report, which will then be signed and retained.

The electronic file of the 12-lead ECG analysis report provided to the sponsor by the central ECG measurement facility will be used as the source document; therefore, entry of the heart rate, RR interval, PR interval, QRS axis, QT interval, and QTc interval (QTcB, QTcF) in the eCRF will be unnecessary.

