7.6.4 Electrocardiogram Data

For 12-lead ECG parameters, measured values and changes from baseline at each time point and at the time of final IMP administration will be summarized using descriptive statistics.

The numbers and percentages of subjects who have a QTc interval (QTcF) of >450 , >480 , or > 500 msec at any post-treatment time point until the time of final IMP administration will be calculated. The numbers and percentages of subjects who have a change in QTc interval from baseline of >30 and >60 msec at any post-treatment time point and at the time of final IMP administration will be calculated. Also at baseline and at each post-treatment time point, the numbers and percentages of subjects will be calculated in the same manner as described above.

Shift tables for QTcF interpretation (normal or abnormal) will be prepared at each post-treatment time point and at the time of final IMP administration compared with baseline.

8 Management of Investigational Medicinal Product

For full details on IMP management, see the OPC-61815 IB and the clinical operation manual.

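### The SAP's QTcF shift table is filled from the site's reading of the whole ECG, so it does not show QTcF shifts

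*SAP*

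**What the plan says.** Protocol 7.6.4 plans the table in these terms: "Shift tables for QTcF interpretation (normal or abnormal) will be prepared at each" post-treatment time point and at final administration, compared with baseline. It does not say whose reading is used, and it gives no QTcF cut-off for normal.

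SAP 9.6 repeats the plan ("Shift tables for QTcF interpretation (normal or abnormal) will be prepared at each post-treatment time point") and names the source: "Interpretation (normal or abnormal) assessments by the trial site (investigator or subinvestigator) will be used instead of the assessments" by the central ECG laboratory.

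Protocol 3.7.3.4 describes what each party produces:

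- **Site.** "The investigator or subinvestigator will interpret each ECG chart as normal or abnormal". What goes into the eCRF is the "interpretation (normal or abnormal [details, if abnormal"]). Once the central report arrives, the investigator "will reconfirm the interpretation of the 12-lead ECG referring to the analysis report".
- **Central facility.** "The ECG record will be sent to the central ECG measurement facility to measure the heart rate, RR interval, PR interval", and the list goes on to QTcB and QTcF. These values reach the sponsor as an electronic file and are not entered in the eCRF.

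The only ECG shift table listed in SAP Appendix 1 is CT-12.2. Its title refers to 12-lead ECG findings and does not mention QTcF.

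SAP 9.6 also plans QTcF threshold counts at 450, 480 and 500 msec and counts of QTc change above 30 and 60 msec, at any post-treatment time and by visit. The threshold counts are also produced at baseline.

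**The concern.** The label and the source of the table disagree. The label says QTcF. The source is a single binary judgement on the whole tracing, which can be abnormal because of rhythm, pacing, conduction or anything else. Neither document describes a site reading of QTcF as normal or abnormal.

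Two errors of interpretation follow. A subject whose baseline chart was abnormal for another reason stays in the abnormal-to-abnormal cell if QTcF becomes prolonged, so the table shows no shift. A subject whose baseline chart was normal can move to abnormal for a reason unrelated to QTcF, and under the present label that move would be read as a QTcF shift. A reader of the study report could take a quiet table as reassurance about QTcF, or a busy one as a signal, and neither would be justified.

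**Working it through.** The plan states no figure on this point, so the check is mainly a trace of the data, followed by one range calculation.

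**1. Trace of the variable**

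| Step | Place | Content |
|---|---|---|
| Label | Protocol 7.6.4, SAP 9.6 | QTcF, normal or abnormal |
| Named source | SAP 9.6 | Site normal/abnormal assessment |
| What the site assesses | Protocol 3.7.3.4 | The whole ECG chart, one reading per ECG |
| Where QTcF is measured | Protocol 3.7.3.4 | Central facility only |
| Listed output | SAP Appendix 1, CT-12.2 | Shift in 12-lead ECG findings |

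The last four rows agree with each other; the label does not agree with them.

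**2. What a binary whole-chart table can show**

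- Baseline abnormal: the only possible cells are abnormal to abnormal and abnormal to normal. A new QTcF abnormality cannot appear as a shift.
- Baseline normal: a move to abnormal can come from any ECG finding, so it does not identify QTcF.

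**3. What the other QTcF outputs recover**

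- The threshold counts at baseline and at each visit are marginal totals. Suppose one subject rises from 450 msec or below to above 450, and another falls the opposite way. The count above 450 is one before and one after. Two subjects who stay where they are, one above and one below, give the same counts.
- The any-time count, as worded, is not restricted to subjects below the threshold at baseline. It combines new with pre-existing exceedance.
- The change counts are within-subject and recover part of this. A move from 450 or below to above 480 exceeds 480 − 450 = 30 msec and must enter the >30 msec count. A crossing of one threshold by 30 msec or less does not, and the change count never says which threshold was crossed.

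What remains missing is the joint baseline-by-post table.

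**4. How many subjects could be affected**

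Inputs: 144 planned subjects per group (Protocol 7.1), used only as a denominator, and p, the proportion with an abnormal baseline ECG. The documents do not give p, so it is an assumption. Subjects per arm who cannot show a new abnormality = 144 × p; those who can = 144 × (1 − p).

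| Assumed p | Cannot show a new abnormality | Can |
|---|---|---|
| 30% | 43.2 | 100.8 |
| 50% | 72.0 | 72.0 |
| 70% | 100.8 | 43.2 |
| 90% | 129.6 | 14.4 |

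The defect exists for any p above zero; p sets only its extent.

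**The case against.** The best reply is that the word QTcF is a slip. Protocol 7.6.4 gives no cut-off for a normal QTcF. In 3.7.3.4, interpretation as normal or abnormal always means the investigator's reading of the ECG, and CT-12.2 is already titled that way. On this view the intended table is the whole-ECG shift and only the label needs correcting. That is a plausible account of how the wording arose, and it is why a reader should not conclude that a defined QTcF shift analysis has been dropped: the documents never defined one. It does not rescue the text, because both documents still name QTcF and the SAP records no change from the protocol.

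The second reply is that QTcF is well covered elsewhere. This stands. A reader might infer that the SAP discards the central ECG data, or that QTcF prolongation would go unseen in a subject with, say, atrial fibrillation. SAP 9.6 supports neither inference. What "will be used instead of the assessments by the central ECG analysis laboratory" is only the site's normal/abnormal call; central QTcF measurements remain the only described source for the descriptive statistics, threshold counts and change counts. Such a subject would enter the threshold count whatever the baseline chart looked like. Individual central results are also listed (PDATA-6.1).

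Third, the site reading is reconfirmed with the central report in view and carries details when abnormal. It is therefore informed by QTcF, but it remains one reading per ECG, and no coding or tabulation of the details is planned.

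Finally, a reader might suppose that most baseline ECGs in this population will be abnormal and the table nearly empty. Arrhythmia, pacemaker and defibrillator status are collected at screening, which makes abnormal baselines plausible, but the documents give no rate.

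**Conclusion.** The point holds, at minor severity. As written, SAP 9.6 presents a whole-ECG reading under a QTcF label. The table does not measure QTcF shifts, and a subject with an abnormal baseline ECG cannot register a new QTcF abnormality in it.

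The loss is confined to the within-subject baseline-by-post cross-tabulation of QTcF, which is what would separate new from pre-existing exceedance of a threshold. The primary analysis is unaffected.

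The number of subjects concerned is unknown. The range of about 43 to 130 of 144 per arm rests entirely on the assumed 30% to 90% of abnormal baseline ECGs and on the planned group size. The conclusion also assumes that the site makes no QTcF-specific normal/abnormal call beyond what Protocol 3.7.3.4 describes.

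**What to change.** In SAP 9.6:

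1. Build the QTcF shift table from the central QTcF values, baseline against each post-treatment time point and final administration, using the section's own cut-offs as bands: ≤450, >450 to 480, >480 to 500 and >500 msec. Add it to Appendix 1.
2. Describe the site-based table as a shift in overall 12-lead ECG findings, consistent with the existing title of CT-12.2.

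The cost is a wording edit and one extra descriptive table from data already held, with no new collection. If the sponsor wants only the site reading tabulated, the minimum is to remove QTcF from the label and record in SAP section 14 that this departs from the wording of Protocol 7.6.4; the cross-tabulation would then stay missing.

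Separately, SAP 9.6 has lost the greater-than sign before 480, which Protocol 7.6.4 has. That is a typographical correction for the same edit and no part of the argument above.

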9.7 Other Safety Data

None.

10 Pharmacokinetic Analyses

10.1 Endpoints

Plasma concentrations of OPC-61815 free form and tolvaptan (OPC-41061)

10.2 Analysis Set

Pharmacokinetic Analysis Set

10.3 Handling of Data

- 1) Plasma concentrations below lower limit of quantitation that occur prior to and after the first measurable concentration will be imputed to 0 (ng/mL) and missing. Lower limit of quantitation of each analyte is listed in 3. Missing for plasma concentrations will not be imputed.

10.4 Statistical Analyses

The plasma drug concentration data will be summarized using descriptive statistics as follows:

- At each time point, the plasma drug concentration data will be summarized by compound and by treatment group using descriptive statistics.
- The descriptive statistics to be calculated include number of subjects (n), mean, SD, coefficient of variation, minimum, median, and maximum.

11 Pharmacodynamic Analyses

A pharmacodynamic analysis will be conducted on the pharmacodynamic analysis set.

For the following endpoints, measured values and changes from baseline at each time point will be summarized by treatment group using descriptive statistics (n, mean, SD, minimum, median, and maximum). For changes from baseline in daily urine volume, daily fluid intake, and daily fluid balance after IMP administration on Day 1 and after IMP administration on Day 5, the mean difference ([OPC-61815 16-mg injection group] – [tolvaptan 15-mg tablet group]) and its 95% CI (based on the t distribution) will be calculated. For daily urine volume after IMP administration, the mean changes from baseline after IMP administration on Day 1 and after IMP administration on Day 5 and their two-sided 95% CIs (based on the t-distribution) will be calculated.

For daily urine volume, a transition chart of measurements (mean \pm SD) from the run-in period to Day 5 will be created in each group. For changes from baseline after IMP administration on Day 1 and after IMP administration on Day 5, a bar graph of the mean (two-sided 95% CI) with the horizontal axis representing treatment groups will also be created.

- Daily urine volume
- Daily fluid intake
- Daily fluid balance
- Serum sodium concentration, serum potassium concentration
- Serum osmolality
- Biomarkers (plasma arginine vasopressin [AVP] concentration, plasma brain natriuretic peptide [BNP] concentration, plasma renin activity, serum NT-proBNP concentration, and serum troponin I concentration)
- Daily urine sodium excretion
- Daily urine potassium excretion
- Urine osmolality

12 Pharmacogenomic Analyses

No pharmacogenomic analysis will be performed in this trial.

13 Interim Analysis

No interim analysis will be performed in this trial.

14 Changes in the Planned Analyses

None.

15 References

None.

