1) Pharmacokinetics and Pharmacodynamics

Following a single intravenous administration of OPC-61815 at 2, 4, 8, or 16 mg, the mean C_{max} , AUC_{24h} , AUC_t , and AUC_∞ values of OPC-61815 free form and tolvaptan increased in a dose-dependent manner. The median t_{max} values of OPC-61815 free form and tolvaptan were from 1.03 to 1.04 and 1.48 to 1.76 hours, respectively, and the mean $t_{1/2,z}$ values were from 1.8 to 3.8 hours and 7.4 to 8.6 hours. The mean CL and V_z values of OPC-61815 free form were from 4.29 to 5.50 L/h and 10.5 to 24.7 L, respectively. The mean ratios of AUC_{24h} , AUC_t , and AUC_∞ for tolvaptan to OPC-61815 free form were from 0.846 to 1.42, 0.847 to 1.45, and 0.989 to 1.77, respectively. Repeated intravenous administration of OPC-61815 at 2, 4, 8, or 16 mg once daily for 5 consecutive days resulted in no accumulation of OPC-61815 free form but an approximately 1.2- to 1.4-fold accumulation of tolvaptan. Tolvaptan exposure (C_{max} and AUC_{24h}) on Day 1, which was the primary variable, following single intravenous administration of OPC-61815 at 16 mg was the closest and similar to that following single administration of tolvaptan 15 mg tablet. Tolvaptan accumulated approximately 1.3-fold by repeated administration of tolvaptan 15 mg tablet once daily for 5 consecutive days, which was similar to the accumulation following repeated intravenous administration of OPC-61815 at 16 mg once daily for 5 consecutive days. The pharmacokinetic parameters of metabolites DM-4103 and DM-4107 after a single intravenous administration and repeated intravenous administration of OPC-61815 at 16 mg were similar to those after a

single oral administration and repeated oral administration of tolvaptan 15-mg tablet, respectively.

When OPC-61815 was intravenously administered at 2, 4, 8, or 16 mg once daily for 5 days, the daily urine volume increased from baseline in all dose groups on the day after start of IMP administration and onward.

2) Efficacy and Safety

The changes (mean \pm standard deviation [SD]) in body weight from baseline at time of final IMP administration were -0.6 ± 0.6 kg in the OPC-61815 2-mg group, -1.1 ± 0.8 kg in the OPC-61815 4-mg group, -1.5 ± 1.1 kg in the OPC-61815 8-mg group, -2.1 ± 1.8 kg in the OPC-61815 16-mg group, and -1.7 ± 1.2 kg in the tolvaptan 15-mg tablet group; body weight decreased from baseline in all treatment groups.

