6.3 Pharmacodynamics

A pharmacodynamic analysis will be conducted on the pharmacodynamic analysis set (see [Section 7.2](#)).

For the following endpoints, measured values and changes from baseline at each time point will be summarized by treatment group using descriptive statistics (n, mean, SD, minimum, median, and maximum). For changes from baseline in daily urine volume, daily fluid intake, and daily fluid valance after IMP administration on Day 1 and after IMP administration on Day 5, the mean difference ([OPC-61815 16-mg injection group] – [tolvaptan 15-mg tablet group]) and its 95% CI will be calculated.

- Daily urine volume
- Daily fluid intake

- Daily fluid balance
- Serum sodium concentration and sodium potassium concentration
- Serum osmolality
- Biomarkers (plasma AVP concentration, plasma BNP concentration, plasma renin activity, serum NT-proBNP concentration, and serum troponin I concentration)
- Daily urine sodium excretion
- Daily urine potassium excretion
- Urine osmolality

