9.3	Clinical Laboratory Data	18
9.4	Vital Sign Data	18
9.5	Physical Examination Data	18
9.6	Electrocardiogram Data.....	19
9.7	Other Safety Data	19
10	Pharmacokinetic Analyses.....	19
10.1	Endpoints.....	19
10.2	Analysis Set.....	19
10.3	Handling of Data	19
10.4	Statistical Analyses	19
11	Pharmacodynamic Analyses.....	20
12	Pharmacogenomic Analyses	20
13	Interim Analysis	21
14	Changes in the Planned Analyses	21
15	References	21

List of Appendices

Appendix 1	List of Summary Tables.....	22
Appendix 2	List of Subject Data Listings	29
Appendix 3	Molecular Weight and Lower Limit of Quantification for Plasma Drug Concentrations	31

List of Abbreviations and Definition of Terms

Abbreviation	Definition
AE	Adverse event
ANCOVA	Analysis of covariance
AVP	Arginine vasopressin
BNP	Brain natriuretic peptide
CHF	Congestive heart failure
CRF	Case report form
ICH	International Conference on Harmonisation
IMP	Investigational medicinal product
MedDRA	Medical Dictionary for Regulatory Activities
NYHA	New York Heart Association
PT	Preferred Term
SOC	System Organ Class
TEAE	Treatment-emergent adverse event
ULN	Upper limit of normal

1 Introduction

This statistical analysis plan documents the details of the statistical analysis methodology to be applied in the protocol of Trial 263-102-00003.

2 Trial Objectives

Primary: To confirm the non-inferiority of OPC-61815 16-mg injection to tolvaptan 15-mg tablet using as the primary endpoint the change in body weight following 5-day intravenous administration of OPC-61815 16-mg injection or 5-day oral administration of tolvaptan 15-mg tablet to congestive heart failure (CHF) patients with volume overload despite having received diuretics other than vasopressin antagonists.

Secondary: To evaluate other efficacy endpoints and the safety, pharmacodynamics, and pharmacokinetics of OPC-61815 16-mg injection in comparison with tolvaptan 15-mg tablet.

3 Trial Design

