3.4 Handling of Time Points

Case report form (CRF) Visit values at each time point (run-in period, treatment period, and follow-up) will be used in summaries (but values at the time of discontinuation will not be used in summaries). Unscheduled Visit values will not be used.

Baseline and final administration time point for each variable are defined as follows.

Variable	Baseline ^a	Final Administration Time Point
Body weight	Before IMP administration on Day 1	Day after final IMP administration
Congestive symptoms (lower limb edema, jugular venous distension, hepatomegaly, pulmonary rales, third cardiac sound)	Run-in period (final measurement)	Day after final IMP administration
Pulmonary congestion, cardiothoracic ratio	Run-in period	Day after final IMP administration
NYHA classification	Run-in period	Day after final IMP administration
Clinical laboratory value	Before IMP administration on Day 1	Day after final IMP administration
Vital signs	Before IMP administration on Day 1	Day after final IMP administration
12-lead ECG	Before IMP administration on Day 1	Day after final IMP administration
Serum sodium concentration, serum potassium concentration, serum osmolality, biomarker	Before IMP administration on Day 1	-
Daily urine volume, daily fluid intake, daily fluid balance, daily urine sodium excretion, daily urine potassium excretion, urine osmolality	Within 24 hours before start of IMP administration on Day 1	-

^aWhen multiple data are collected during the run-in period, the data closest to Day 1 will be used as baseline.

4 Sample Size

The number of subjects required to confirm the non-inferiority of OPC-61815 16-mg injection to tolvaptan 15-mg tablet for the primary endpoint of change in body weight from baseline (before IMP administration on Day 1) at the time of final IMP administration (day after final IMP administration) was determined.

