8.1.1 Primary Efficacy Analysis

Main analysis is an analysis of the primary endpoint using an ANCOVA model with treatment as a fixed effect factor and baseline body weight as a covariate. The least square mean difference and its two-sided 95% CI (based on the t distribution) between the OPC-61815 16-mg injection group and the tolvaptan 15-mg tablet group will be calculated. The non-inferiority of OPC-61815 16-mg injection to tolvaptan 15-mg tablet will be confirmed when the upper limit of the CI does not exceed 0.48.

At each time point, the measured values, changes, and percent changes in body weight from baseline will be summarized by treatment group using descriptive statistics.

Using the main analysis model excluding baseline body weight, the least-square mean of the difference between the OPC-61815 16-mg injection group and the tolvaptan 15-mg group and its two-sided 95% CI will also be calculated.

For changes in body weight from baseline, a timecourse (mean \pm SD) from Day 1 of treatment period to follow-up will be created for each treatment group.

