8.3.2 Jugular Venous Distension, Hepatomegaly, and Cardiotoracic Ratio

The changes in jugular venous distension, hepatomegaly, and cardiotoracic ratio from baseline at time of final IMP administration will be analyzed using an ANCOVA model with treatment as a fixed effect factor and baseline body weight as a covariate, and the least-square mean differences and their two-sided 95% CIs (based on the t distribution) between the OPC-61815 16- mg injection group and the tolvaptan 15-mg tablet group

will be calculated. In addition, at each time point, measured values and changes from baseline will be summarized by treatment group using descriptive statistics. For jugular venous distension and hepatomegaly, the time course of changes from baseline to each time point will be plotted (mean \pm SD). Note that the absence of jugular venous distension and hepatomegaly will be indicated as 0 cm. The above data on jugular venous distension and hepatomegaly will also be summarized for subjects with baseline value and the time course will be plotted in the same manner. For the presence/absence of jugular venous distension and hepatomegaly, shift tables in changes from baseline at the final IMP administration and at each timepoint following IMP administration will be prepared by each treatment group.

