CT-10.5 Incidence of Potential Drug-Induced Liver Injury (Safety Analysis Set)

CT-11 Mean Change from Baseline in Vital Signs (Safety Analysis Set)

CT-12.1 Mean Change from Baseline in Electrocardiogram Results (Safety Analysis Set)

CT-12.2 Shift Table of 12-Lead ECG Findings (Normal/Abnormal Assessments) (Safety Analysis Set)

CT-12.3.1 Incidence of Categorical Changes in Electrocardiogram Results (Post baseline any visit) (Safety Analysis Set)

CT-12.3.2 Incidence of Categorical Changes in Electrocardiogram Results (Each Visit) (Safety Analysis Set)

PDT-1.1 Descriptive Statistics for Daily Urine Volume (mL) With Confidence Interval for Treatment Difference (Pharmacodynamic Analysis Set)

PDT-1.2 Mean Change for Daily Urine Volume (mL) With Confidence Interval for Each Treatment Group (Pharmacodynamic Analysis Set)

PDT-2 Descriptive Statistics for Daily Fluid Intake (mL) With Confidence Interval for Treatment Difference (Pharmacodynamic Analysis Set)

PDT-3 Descriptive Statistics for Daily Fluid Balance (mL) With Confidence Interval for Treatment Difference (Pharmacodynamic Analysis Set)

PDT-4 Descriptive Statistics for Serum Sodium Concentration (mEq/L) (Pharmacodynamic Analysis Set)

PDT-5 Descriptive Statistics for Serum Potassium Concentration (mEq/L) (Pharmacodynamic Analysis Set)

PDT-6 Descriptive Statistics for Serum Osmolality (mOsm/kg) (Pharmacodynamic Analysis Set)

PDT-7 Descriptive Statistics for Plasma AVP Concentration (pg/mL) (Pharmacodynamic Analysis Set)

PDT-8 Descriptive Statistics for Plasma BNP Concentration (pg/mL) (Pharmacodynamic Analysis Set)

PDT-9 Descriptive Statistics for Plasma Renin Activity (ng/mL/hr) (Pharmacodynamic Analysis Set)

PDT-10 Descriptive Statistics for Serum pro BNP Concentration (pg/mL) (Pharmacodynamic Analysis Set)

PDT-11	Descriptive Statistics for Serum Troponin Concentration (pg/mL) (Pharmacodynamic Analysis Set)
PDT-12	Descriptive Statistics for Daily Urine Excretion of Sodium (mEq) (Pharmacodynamic Analysis Set)
PDT-13	Descriptive Statistics for Daily Urine Excretion of Potassium (mEq) (Pharmacodynamic Analysis Set)
PDT-14	Descriptive Statistics for Urine Osmolality (mOsm/kg) (Pharmacodynamic Analysis Set)
CF-1	Transition Diagram for Body Weight (Full Analysis Set)
CF-2	Transition Diagram for Improvement Rate of Lower Limb Edema (Full Analysis Set)
CF-3.1	Transition Diagram for Jugular Venous Distension (cm) (Full Analysis Set)

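### Day 1 and Day 5 group differences in urine volume, fluid intake and fluid balance leave out each variable's own baseline as a covariate: a cheap possible gain in precision, of unknown size and possibly nil

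*SAP*

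**What the plan says.** The SAP's secondary objective is "To evaluate other efficacy endpoints and the safety, pharmacodynamics, and pharmacokinetics of OPC-61815 16-mg injection" against the tablet, so the pharmacodynamic comparison is part of a stated objective. Under SAP section 11, most pharmacodynamic variables get descriptive statistics only. Three also get a between-group estimate: "For changes from baseline in daily urine volume, daily fluid intake, and daily fluid balance after IMP administration on Day 1", and again after the Day 5 dose, the difference in means between injection and tablet is reported with a 95% CI based on the t distribution. Protocol 6.3 has the same estimator ("after IMP administration on Day 5, the mean difference"). Neither text names a model or covariate, and the outputs (PDT-1.1, PDT-2, PDT-3) are titled as descriptive statistics with a CI for the treatment difference.

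SAP 3.4 defines the baseline of these variables as "Within 24 hours before start of IMP administration on Day 1", so a baseline value is collected for each.

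Elsewhere the SAP does use covariates. The primary body-weight analysis (SAP 8.1.1) is made "using an ANCOVA model with treatment as a fixed effect factor and baseline body weight as a covariate". SAP 8.3.2 applies a model with the same covariate, baseline body weight, to "The changes in jugular venous distension, hepatomegaly, and cardiotoracic ratio from baseline at time of final IMP administration".

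**The concern.** Subtracting the baseline fixes the slope of the post-dose value on baseline at 1. ANCOVA estimates that slope from the data. If the true slope is not 1, the change score over- or under-corrects for chance differences in baseline between the groups, and its interval carries variance that the collected baseline could remove.

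The stake is limited. The planned estimate is fully specified, unbiased under randomization, and has a valid interval. No general SAP rule is broken: body weight is adjusted for its own baseline, but the three endpoints in SAP 8.3.2 are adjusted for baseline body weight and not for their own. However, these are the only pharmacodynamic variables with a between-group interval. The width of that interval is what a reader will use to judge how closely injection and tablet agree on urine volume and fluid balance.

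**Working it through.** **Inputs from the documents.** 144 per group, 288 in total (SAP section 4); 1:1 allocation (protocol 3.6.1). There is no SD, correlation or power for urine volume, fluid intake or fluid balance.

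**The plan's own figure.** The only sample-size calculation is for body weight: margin 0.48, SD 1.25, true difference 0, 90% power, 5% two-sided. Per group, 2 × [1.25 × (1.960 + 1.282) / 0.48]² = 142.5, so 143; the noncentral-t version gives 144. The stated 288 reproduces. It does not depend on the point here, but it supplies the N used below.

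**Formula.** Let r be the within-group correlation of baseline with post-dose value and k = SD(baseline)/SD(post-dose), both taken as equal in the two groups. Scale the post-dose SD to 1.
- Variance of the change score: 1 + k² − 2rk.
- Residual variance after ANCOVA on own baseline: 1 − r².
- Their difference: (k − r)², which is never negative and is zero only when r = k, that is, when the slope r/k equals 1.
- CI width ratio, adjusted to unadjusted: √[(1 − r²)/(1 + k² − 2rk)].

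**Narrowing of the 95% CI (r and k are assumptions).**

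| k | r = 0.3 | r = 0.5 | r = 0.7 |
|---|---|---|---|
| 1 | 19.4% | 13.4% | 7.8% |
| 0.8 | 11.4% | 5.5% | 1.0% |
| 0.5 | 2.1% | 0.0% | 3.7% |

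Example: for r = 0.3, k = 1, √(0.91/1.40) = √0.65 = 0.806. In sample-size terms, the k = 1 row runs from 144/0.85 = 169 per group (r = 0.7) to 144/0.65 = 222 per group (r = 0.3) for an unadjusted analysis of equal precision.

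**The grid is not a bound.** r = 0, k = 1 gives 29.3%; r = 0.9, k = 0.5 gives 26.3%; r = 0.3, k = 1.25 gives 29.1%.

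**Cost when there is no gain.** Estimating one covariate slope at N = 288 multiplies the width by √(1 + 1/284) = 1.0018, or about 0.2%. Adjustment therefore fails to pay only when (k − r)² is below (1 − r²)/284. At r = 0.5 that means k within √(0.75/284) = 0.05 of 0.5.

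**Simulation check**, 144 per group, 6000 runs per setting, mean width ratio adjusted/unadjusted:

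| r, k | Simulated | Formula |
|---|---|---|
| 0, 1 | 0.709 | 0.707 |
| 0.9, 0.5 | 0.739 | 0.737 |
| 0.3, 1 | 0.808 | 0.806 |
| 0.5, 0.8 | 0.947 | 0.945 |
| 0.5, 0.5 | 1.002 | 1.000 |

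Coverage of both intervals was 94.4% to 95.2%.

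**Urine volume.** Protocol 1.2.2 reports that in phase 2 "the daily urine volume increased from baseline in all dose groups". If spread rises with the mean, which is an assumption, k is below 1 for this variable; the k = 0.5 row gives 0 to 4%.

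**The case against.** The best reply is that this is a preference and not a fault. The plan is valid, SAP and protocol agree on the estimator, and the intervals sit among descriptive summaries with no hypothesis, margin or power. Every percentage above rests on assumed r and k, and a different grid gives a different range. The phase 2 remark on urine volume reports no spread, so it fixes no value of k. Adjustment also loses two properties. Fluid balance is intake minus urine volume (protocol 3.7.5.2.3), so in subjects with all values the unadjusted differences add up exactly. The unadjusted urine difference also matches the group means planned in PDT-1.2 ("Mean Change for Daily Urine Volume (mL) With Confidence Interval for Each Treatment Group") and in figure CF-7.

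Most of this stands. The point is not an error, its size cannot be determined from the documents, and no average over the grid should be read as an expected gain. What the reply does not remove is the imbalance between cost and benefit: about 0.2% in width at worst against a gain that may be material, with the lost properties recovered by keeping the unadjusted difference alongside.

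**Conclusion.** The point holds as an optional improvement. The Day 1 and Day 5 differences for the three variables use the baseline only by subtraction, and own-baseline ANCOVA is never less precise in large samples when r and k are common to both groups. The size of the gain is unknown: 0 to 19% narrower over the assumed grid, more at some values outside it, and nil when r = k, where the adjusted interval is about 0.2% wider at 144 per group. Nothing in the primary analysis, its margin or the sample size depends on it. Confidence is medium, because the benefit rests on quantities that the documents do not give.

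**What to change.** In SAP section 11, before unblinding, take the Day 1 and Day 5 between-group differences and 95% CIs for daily urine volume, fluid intake and fluid balance from an ANCOVA of change, with treatment as factor and the variable's own 24-hour baseline as covariate. Keep the unadjusted mean difference with its t interval as supportive, and keep all descriptive statistics. Record the change in SAP section 14, which now lists none, and align protocol 6.3 at any next amendment.

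The cost is SAP wording, the section 14 entry, and one model statement for PDT-1.1, PDT-2 and PDT-3. Six between-group intervals (three variables, two days) become twelve. No new data are needed, and no subject with a change value drops out, because a change value already requires the baseline. Until an amendment is made, the SAP would differ from protocol 6.3, as disclosed in section 14. The three adjusted differences will not add up exactly, and the adjusted urine difference will not match PDT-1.2 and CF-7; the retained unadjusted differences serve both purposes.
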